## APPLICATION NARRATIVE

### A. PROPOSED RESEARCH RATIONALE

The Supplemental Nutrition Assistance Program-Education (SNAP-Ed) is an educational program offered to SNAP participants. The Nutrition Education Program (NEP) through Purdue University Health and Human Sciences Extension administers SNAP-Ed in Indiana. The NEP curriculum comprises 10 lessons that are focused on nutrition and food resource management.

The goal of this study is to determine the efficacy of SNAP-Ed to improve the immediate and long-term dietary quality (using the Healthy Eating Index (HEI)), BMI (measured height and weight), and food security (using the 18-item US HFSSM) and how the provision of SNAP-Ed with the presence of other characteristics can mediate improvement in these outcomes. Previous studies by [name] have shown significant improvements in household food security over short-term periods and a 1-year longitudinal period among Indiana NEP participants; however, the impact of SNAP-Ed on participants' dietary quality and BMI remains to be investigated. The hypothesis of this study is that dietary quality and food security will improve and BMI will remain steady over the short-term, and these improvements will be maintained over a 1-year, or "long-term", time frame in participants receiving SNAP-Ed compared to those not receiving SNAP-Ed. Results may be used as a basis for changes to the program or policies relevant to SNAP-Ed and other nutrition education programs throughout the US.

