### B. SPECIFIC PROCEDURES TO BE FOLLOWED

NEP educators are considered key personnel because they will have direct contact with study participants; however, they will not have any part in data entry, analysis, or dissemination of study results. NEP educators, employees of Purdue University Extension, across Indiana will help facilitate the study. NEP educators have completed CITI training as a requirement for employment through Purdue University Extension. Before recruiting study participants, participating NEP educators will attend training sessions facilitated by the co-investigators of the study. The training sessions will include instructions on how to interact with participants; answer questions related to the study; and protocol for administering surveys, measuring height and weight, keeping participant information private, and the use of identification numbers. The study goals and hypothesis will not be shared with the NEP educators in order to keep their work with the participants as unbiased as possible.

NEP educators will recruit study participants who are interested in participating in NEP. The details of recruitment are described in Section D. A screening survey determining eligibility will be administered in addition to an explanation of consent. After completion of the screening survey and consent process, NEP educators will randomize participants into one of two groups: control or experimental. The NEP educators will be assigned a random number using Excel and then listed in order from least to greatest according to their random number. The first half of the NEP educators will assign their first recruited participants to the experimental group. After the first assignment, they will alternate assigning participants to either study group in an "every other" participant fashion. The second half of the NEP educators will assign their first recruited participants to the control group. After the first assignment, they will also alternate assigning participants to either study group in an "every other" participant fashion. The control group will wait 1 year from taking the second survey before starting NEP lessons. The experimental group will start NEP lessons immediately. Participants in the experimental group must take at least the first 4 NEP lessons within a time period of 4 to 10 weeks. The NEP SNAP-Ed curriculum includes 10 lessons, and participants may take the additional 6 lessons if desired.

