All participants will complete three 30 minute surveys throughout the study. Surveys will be administered by NEP educators using the Qualtrics Offline Application on their program-provided iPads or paper surveys. The first survey will be administered upon enrollment in the study. Participants in the experimental group will take the second survey after they have completed the first 4 lessons between 4 and 10 weeks after enrollment in the study. Control participants will take the second survey after 4 to 10 weeks with no lessons. Since participants will be recruited on a rolling basis, they will take surveys at different times within a designated time

period. The third survey will be administered to both groups 1 year after the second survey. Surveys are comprised of the US Household Food Security Survey Module from the United States Department of Agriculture Economic Research Service, questions querying household and individual level characteristics, and the Indiana Food and Nutrition Program Evaluation Tool.

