
In addition to the survey, dietary recalls, and FFQ, NEP educators will take height and weight measurements on each participant at each assessment time point. Weights will be measured using the SECA 869 mobile medical flat scale with remote display. Heights will be measured using the SECA 213 mobile stadiometer. This weight scale and stadiometer are research grade measurement tools. Height and weight measurements will be taken following the Centers for Disease Control and Prevention (CDC) National Health and Nutrition Examination Survey (NHANES) anthropometry manual guidelines. Height and weight measurements will be completed in a private setting or privacy screens will be used. Only the NEP educators will be able to see the measurements. Three measurements will be taken at each assessment time point in order to calculate an average. Participants will be allowed to know their measurements upon request at the time of measurement. Researchers will use these measurements to calculate BMI.

An in person survey, two dietary recalls, one FFQ, and height and weight measurements will be completed for each participant at each of the three assessment time points. The first and third assessments will cover a reference period the past 12 months, while the second assessment will cover the past 30 days. Participants randomized to the control group will be provided the opportunity to complete the SNAP-Education program at the completion of the study.

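### As worded, the second survey follows four completed lessons in the experimental arm but elapsed time in the control arm, and the plan does not settle how participants without four lessons by week 10 are assessed or analysed

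*Protocol*

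**What the plan says.** All of the timing text is in Protocol section B.

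- Experimental arm, second survey: "Participants in the experimental group will take the second survey after they have completed the first 4 lessons between 4 and 10 weeks after enrollment".
- Control arm, second survey: "Control participants will take the second survey after 4 to 10 weeks with no lessons".
- Both arms, third survey: "The third survey will be administered to both groups 1 year after the second survey".
- Lesson requirement: "Participants in the experimental group must take at least the first 4 NEP lessons within a time period of 4 to 10 weeks". No consequence is given for someone who does not meet it.
- Control arm's access to lessons: "The control group will wait 1 year from taking the second survey before starting NEP lessons".

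Two statements in the same section point the other way. One is "All participants will complete three 30 minute surveys throughout the study". The other says that the survey, recalls, food frequency questionnaire, height and weight "will be completed for each participant at each of the three assessment time points".

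On who is compared, section A words the hypothesis by receipt of the program: "in participants receiving SNAP-Ed compared to those not receiving SNAP-Ed". The SAP words its diet-quality and nutrient comparisons by intervention and control group. It names no analysis set and gives no rule for non-adherence or missing data. Its nearest text (Characteristics) is a descriptive comparison of people who withdrew with people who completed the study, and it does not say which of these a person who stops lessons is.

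**The concern.** One arm's assessment is worded as depending on something participants do after allocation; the other arm's depends only on the calendar. Because the third survey is dated from the second, the condition can carry through to one year. That is the endpoint of the SAP's nutrient-change outcome and of its long-term comparison of the proportions at risk of inadequacy. It may also bear on diet quality, where change is assessed over time without named time points.

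An educator whose participant stopped at lesson 3, or is due to finish lesson 4 in week 11, could reasonably follow either instruction, and different educators could differ. If the lesson condition is followed, the experimental arm shrinks to people who kept attending while the control arm does not. That biases the comparison if attendance is related to change in diet. A reader of the results could not tell from these documents which practice was used.

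**Working it through.** **Step 1. Set the rules side by side.**

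| Participant | Second survey | Third survey |
|---|---|---|
| Control, on schedule | weeks 4–10 | 4 + 52 = 56 to 10 + 52 = 62 weeks after enrollment |
| Experimental, four lessons by week 10 | weeks 4–10 | weeks 56–62 |
| Experimental, fewer than four lessons by week 10 | no date under the lesson condition; required by the all-participants statements | no date, because it runs from the second |
| Either arm, second survey missed for another reason | missed | no date |

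The last row is common to both arms. Only the third row is arm-specific, and it is where the statements in section B conflict.

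**Step 2. Reproduce the plan's own figures (Protocol section C).** 800 × 0.40 = 320 lost and 800 − 320 = 480 final, as stated; that is 240 per arm if the loss is equal. The short-term attrition is 17/236 = 7.2%, stated as 7%. The 40% is not split by arm or by lesson completion, so no lesson-completion rate can be recovered.

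**Step 3. Illustrate what a literal filter could do.** This is an unadjusted two-group comparison with no true effect. The assumptions below are not in the documents.

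- Completion of four lessons c = 0.70 to 0.93. The 93% only borrows the 7% short-term attrition as a rough anchor.
- Completion occurs when a latent standard normal trait exceeds z, the normal quantile at 1 − c. The trait correlates ρ = 0.1 to 0.3 with the outcome.
- Mean trait among completers: λ(c) = φ(z)/c.
- Rejection rate = P(|Z + bias/SE| > 1.96).

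(a) Filter in the experimental arm only, other dropout unrelated to the trait: bias = ρλ(c). If lesson loss is added to the 40%, SE = √(1/240 + 1/(240c)). If it lies inside the 40%, there are 240 per arm and SE = √(2/240) = 0.0913.

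| c | ρ | Bias (SD) | SE, added | Rejects, added | Rejects, inside |
|---|---|---|---|---|---|
| 0.93 | 0.1 | 0.014 | 0.0930 | 5.3% | 5.3% |
| 0.93 | 0.3 | 0.043 | 0.0930 | 7.5% | 7.6% |
| 0.80 | 0.2 | 0.070 | 0.0968 | 11.2% | 12.0% |
| 0.70 | 0.1 | 0.050 | 0.1006 | 7.8% | 8.5% |
| 0.70 | 0.3 | 0.149 | 0.1006 | 31.6% | 37.2% |

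(b) Dropout in both arms on the same trait. With lesson loss added, bias = ρ[λ(0.6c) − λ(0.6)], which runs from 0.006 SD (c = 0.93, ρ = 0.1) to 0.086 SD (c = 0.70, ρ = 0.3); rejection is 5.1% to 13.7%. If lesson loss lies wholly inside the 40%, both arms keep the top 60% of the trait, the bias is 0 and rejection stays at 5%.

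**Step 4. Cross-check with a different set-up.** Let a share q of 240 retained experimental participants be dropped, with outcomes g SD worse than completers'; the bias is q × g. For q = 5% to 30% and g = 0.25 to 0.50, bias is 0.0125 to 0.15 SD and rejection 5.2% to 32.0%. The difference detectable with 80% power, (1.96 + 0.842) × √(1/240 + 1/n), moves only from 0.256 SD (n = 240) to 0.282 SD (n = 168). Any harm is mainly selection, not lost power.

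**The case against.** The strongest reply is that no filter exists. Section B says without exception that everyone completes every assessment, both arms share one window, and no text withholds a survey from anyone or removes lesson non-completers. The lesson clause could simply describe the order of events on the expected path. This stands as a possible reading. It does not remove the conflict, because the general statements give no date for someone who misses the lesson condition.

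Four further points have force.

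- The undated third survey is not peculiar to one arm: a control who misses the second survey is equally undated.
- The second survey is not itself an input to the nutrient-change outcome, which runs from baseline to one year. The filter reaches that outcome only if the third survey is lost too. Section C has educators telephone participants in both arms to arrange the final survey, which helps. But those contacts are placed after the second assessment, so they do not settle the matter for someone who never had one.
- The SAP's group wording is most naturally read as allocated group, and section A is a rationale rather than an analysis-set definition. An explicit statement is still missing.
- Educators receive survey training whose content is not in these documents, so the missing fallback is shown only for the text supplied.

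A reader might infer that the plan excludes lesson non-completers, or that the type I error is about 30% or more. The documents support neither. No passage makes the exclusion, and the 31.6% and 37.2% require low completion, the strongest assumed correlation and unrelated other dropout all together.

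**Conclusion.** The wording conflict is certain; the harm is conditional. If the lesson condition is applied literally, experimental lesson-completers are compared with all retained controls. If everyone is surveyed, there is no such filter. Only the lesson condition is specific to one arm.

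Size and direction cannot be derived. In the illustration, at 93% completion and a correlation of up to 0.3, rejection does not exceed 7.6%; higher values rest on completion rates and correlations with no source in the documents. The sign of the bias follows the assumed sign of the correlation. The SAP's plan to test baseline characteristics in regression models could reduce the bias for measured characteristics, and the illustration leaves that out. The point should be fixed because the correction is cheap and the protocol already plans three paid assessments for every participant.

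**What to change.** 1. **Protocol section B.** State that every experimental participant is assessed within the existing 4–10 week window whether or not four lessons are complete. State that in both arms a missed second assessment does not cancel the third, which is then timed from the date the second was due. The text should define that date, since a window has no single due date.
2. **SAP.** State that the primary comparisons use all participants in their allocated group with available outcome data, regardless of lessons taken; that stopping lessons is not withdrawal from the study; and that any lesson-completer comparison is secondary.
3. **Protocol section A.** Align the hypothesis wording with that population.

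The control arm's wait for lessons is also dated from the second survey. The sponsor must reconcile that sentence with the revised timing; no rule is proposed here.

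**Cost.** Besides the wording, incentives are up to 2 × $35 = $70 per additional participant followed (section E). At the assumed 70–93% completion, 400 × (1 − c) is 120 to 28 people, so at most $8,400 to $1,960, and less with dropout. Educator visits and researcher calls come on top and are not costed. The estimated effect may be smaller because partly exposed participants are included, and anyone who would finish lesson 4 after week 10 is surveyed mid-course.

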Participants will also complete two 24-hour dietary recalls using the Automated Self-Assisted 24-hour recall (ASA-24) and one food frequency questionnaire (FFQ) using the Diet History Questionnaire II (DHQ II) at each data collection time point. Both instruments are online and complementary dietary assessment tools created by the National Cancer Institute and have a respondent and researcher website. Results will be analyzed by the researchers using the researcher website. One dietary recall and the FFQ may be administered by the NEP Educators immediately following the in person survey, or a link to complete the dietary recall and FFQ online will be emailed to the participant within 2 days, or the participant can request to complete the dietary recalls and FFQ over the phone with the co-investigators at Purdue within 7 days after completing the survey. A script will be provided for the Purdue researchers to administer the dietary recalls and FFQ. The completion of the dietary recalls and the FFQ is necessary to perform complex modeling techniques for estimating *usual* dietary intake. The program that administers the dietary recalls assists participants through the recall process using an animated guide with audio and visual cues. Previous research has shown that the majority of Indiana SNAP-Education participants have a computer with high-speed Internet connection in their home or residence. Participants without email, without access to a computer with internet, or with limited computer skills will be instructed to complete the assessments via telephone with assistance from researchers. If assistance from researchers is needed via telephone, participant identifying information will not be collected at that time. Participants will be identified only by their participant identification number, which they will receive upon enrollment in the study. Participants will provide days and time frames over the following week when they will be available to complete the dietary assessments over the phone with Purdue researchers. In addition, participants may call the co-investigator's Purdue office phone number any time after the survey for assistance with completing the dietary assessments. If the first dietary recall and FFQ have not been completed within 4 days after the survey, researchers will call the participant no more than once per day to complete the first dietary recall and FFQ over the phone at that time or to set up appointments to complete the dietary recalls and FFQ over the phone with researchers within the 7 days after completing the in person survey. The second dietary recall should be completed 24 hours after the first dietary recall at the earliest but before 9 days after completing the in person survey. Participants will have the same options as described above to complete the second dietary recall.

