NEP educators will make no more than four coordinated efforts to remind participants of their participation in the study during the one year period between the second assessment and the final assessment. These attempts will also serve to update contact information, which NEP educators normally collect as part of their normal programming. Purdue researchers do not have access to participant names or home addresses. Purdue researchers only have participant names on consent forms and these documents are separated and stored separately from surveys. There is no way for researchers to identify participants or match their surveys with names. All participants in the study are also clients of the NEP Educators because they currently participate in the Nutrition Education Program as a participant in the intervention study group, or will participate at the conclusion of the study because they have indicated that they have the desire to participate as part of eligibility for the research study. The methods for contacting the participants include phone calls from the NEP educators, emails, physical flyers mailed to participants' home addresses, and a raffle. The email and physically mailed flyer will use the same content (attached). NEP educators will either email or physically mail the flyer, not both, depending on which method is preferred by the participant. All contact methods will be the same for control and intervention study group participants and are described below. Researchers will not directly contact participants unless the participant has requested telephone assistance to complete the dietary recalls and FFQ. Participants who have not completed the dietary recalls and FFQ in the amount of time provided will be called and asked if they would like to complete the dietary recalls and FFQ at that time over the phone, if they would like for researchers to resend the email link, or if they would like to make an appointment for researchers to call at a later time to complete the dietary recalls and FFQ over the phone. Participants will also be provided a Purdue telephone number for contacting researchers to complete the dietary recalls and FFQ.

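### Baseline 24-hour recalls are not tied to lesson 1, so in the experimental arm only they can report intake after lessons have begun

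*Protocol*

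**What the plan says.** All the timing rules are in Protocol Section B (Specific Procedures to be Followed).

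- **Lessons.** Arm is assigned after screening and consent. Then "The experimental group will start NEP lessons immediately", whereas "The control group will wait 1 year from taking the second survey before starting NEP lessons".
- **Survey 1.** "The first survey will be administered upon enrollment in the study".
- **Recall 1.** "One dietary recall and the FFQ may be administered by the NEP Educators immediately following the in person survey". This is one option. The others are an emailed link, or a telephone interview up to 7 days after the survey.
- **Recall 2.** It is due "24 hours after the first dietary recall at the earliest but before 9 days after completing the in person survey".
- **Survey 2, experimental arm.** It is taken "after they have completed the first 4 lessons between 4 and 10 weeks after enrollment in the study".

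Under its Diet Quality heading the SAP makes between-arm change in diet quality a primary outcome, and it scores HEI-2010 from the ASA-24 recalls. Under Nutrient Intake it makes change in mean usual intake from baseline to 1 year another. It gives no rule, count or analysis for baseline recalls that follow a lesson.

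**The concern.** Both primary outcomes measure change from a baseline that should describe diet before the intervention. The recall windows are anchored to the survey and to recall 1. Lesson 1 is anchored to neither. In the experimental arm, then, a baseline recall can describe food eaten after teaching has started. In the control arm this cannot happen at baseline.

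If lessons improve diet early, part of the effect moves into the experimental baseline and is subtracted from the change. The between-arm difference is then most likely too small, and a null result could partly reflect the order of measurement. If lessons alter only how people report food, the direction is unclear. As the plan stands, the trial could not tell afterwards whether any of this had happened.

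**Working it through.** **The plan's own figure.** Section C expects 800 × (1 − 0.40) = 480 completers, which reproduces. Its short-term attrition is 17/236 = 7.2%, stated as 7%. The point does not depend on these numbers. The documents give no significance level, power, effect size or standard deviation, so no consequence for power can be derived.

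**Step 1: which schedules are permitted.** Let the survey be day 0. Section B allows recall 1 on days 0 to 7, and recall 2 from the next day to day 8. The number of day pairs is 8 + 7 + 6 + 5 + 4 + 3 + 2 + 1 = 36. The protocol does not say which 24 hours a recall covers; assume the previous day. A recall on day r then reports day r − 1. It is exposed if r − 1 ≥ L, where L is the day of lesson 1, or if r − 1 > L when the lesson day itself is not counted.

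| Lesson 1 on day | Recall 1, lesson day counted | Recall 2, lesson day counted | Recall 1, lesson day not counted | Recall 2, lesson day not counted |
|---|---|---|---|---|
| 0 | 28/36 = 78% | 36/36 = 100% | 21/36 = 58% | 35/36 = 97% |
| 3 | 10/36 = 28% | 30/36 = 83% | 6/36 = 17% | 26/36 = 72% |
| 7 | 0% | 8/36 = 22% | 0% | 0% |
| 8 or later | 0% | 0% | 0% | 0% |

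These are shares of permitted schedules, not predicted frequencies. They show that overlap needs lesson 1 within about a week of the survey, that recall 2 is more at risk than recall 1, and that recall 1 is not immune. The control arm is 0% in every row.

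**Step 2: what exposure would do.** Treat the two-recall baseline as an average. Let f1 and f2 be the shares of experimental participants whose first and second recalls are exposed. Let e be the fraction of the 1-year effect already present in an exposed recall. The experimental baseline rises by e × (f1 + f2)/2 of the effect, so a change-score contrast shrinks by that proportion. All three inputs are assumed.

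| f1 | f2 | e | Shrinkage |
|---|---|---|---|
| 0 | 0.25 | 0.10 | 0.25/2 × 0.10 = 1.25% |
| 0 | 1 | 0.10 | 1/2 × 0.10 = 5% |
| 0 | 0.5 | 0.25 | 0.5/2 × 0.25 = 6.25% |
| 0 | 0.5 | 0.5 | 0.5/2 × 0.5 = 12.5% |
| 0 | 1 | 0.5 | 1/2 × 0.5 = 25% |
| 0.5 | 1 | 0.5 | 1.5/2 × 0.5 = 37.5% |

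If baseline enters as a covariate instead, the shrinkage is multiplied by the baseline slope, which I assume to be below 1.

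**The case against.** **The overlap may rarely occur.** The wording on starting lessons is set against the control arm's wait and names no day. Four lessons may spread over 4 to 10 weeks. Harm needs lesson 1 soon after the survey, a recall still outstanding, and a change in diet or reporting after very little teaching. All of this stands. The documents permit the overlap; they do not plan it or show that it happens.

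**The order may be fixed elsewhere.** Section M lists recall scripts and Section B describes educator training. Neither was supplied, and either could set the order. This stands as a limit on the claim.

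**The first and third assessments use a 12-month reference period.** That can describe a questionnaire such as the FFQ. It does not help a recall that reports a single day.

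**Late recalls.** A reader might infer from Section C that recalls can run past the window, since it says "Participants who have not completed the dietary recalls and FFQ in the amount of time provided will be called" and offers a later appointment. The documents do not support this. Section B describes similar calls and keeps the resulting recall 1 and FFQ appointments within 7 days of the survey. Section C can be read inside that limit and sets no longer one.

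**The remedy has its own asymmetry.** Arm is assigned before the recalls. Making lessons wait for them gives only experimental participants a reason to finish quickly. This stands, and is why the fix stops short of a strict gate.

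**Conclusion.** The concern holds as a gap in the ordering of measurements. Following the plan as written can let post-lesson intake into the baseline of two primary outcomes, in one arm only. The bias is most likely toward zero if diet improves early. Severity is minor to moderate.

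The size is unknown and may be small. A reader might take 1% to 5% from the working as an estimate. It is not one: it rests on e = 0.10 and a clean first recall, and Section B makes recall at the survey visit optional. Nor are the larger rows a forecast. The documents cannot choose among them.

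Two further readings go too far. One is that the experimental baseline is contaminated throughout, which would need lesson dates the documents do not give. The other is that control recalls are unaffected at every time point; the statement here concerns baseline only.

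**What to change.** 1. Reconcile the lesson-start and recall-timing text in Section B so that baseline dietary assessment precedes the first lesson. Use the existing option of recall 1 and the FFQ at the enrolment visit, before any lesson. Schedule recall 2 before lesson 1 where feasible, with the same recall window and reminders in both arms.
2. Record the date of lesson 1 and the intake date of each recall.
3. Keep all valid baseline recalls in the primary analysis. Do not delete recalls from the experimental arm alone; Section B itself says "The completion of the dietary recalls and the FFQ is necessary to perform complex modeling techniques".
4. Report by arm how many baseline recalls reflect intake after lesson 1, together with baseline recall completion and timing.
5. Add one HEI sensitivity analysis that treats both arms alike, for example using only the first baseline recall. State that it is clean only where recall 1 preceded lesson 1.

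**Cost.** The delay to lesson 1 runs from zero, where it would already follow recall 2, to about nine days, or longer if a group class start is missed. The existing 28-to-70-day period has room: assuming weekly lessons, lesson 1 on day 9 puts lesson 4 on day 9 + 3 × 7 = 30. A few participants may be lost before lesson 1; the documents give no figure, and Section C already expects about 40% attrition. Recall completion may come to differ between arms, which item 4 would show. The recruitment target of 800 is unchanged. The added work is a few date fields, a short table by arm and one analysis.
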